Effects of Er:YAG Photobiomodulation Therapy on Wound Healing of
Human Palatal Mucosa After Connective Tissue Graft Harvesting:
A Pilot Study

NCT03741062

October 16, 2020

STUDY PROTOCOL

Participants

Patients of the Graduate Periodontics Clinic at the University of Manitoba who require a subepithelial connective tissue graft (SECTG) utilizing autogenous donor tissue harvested from the palate, during the time period from Fall 2018 to Spring 2020, and who sign the consent form will be eligible to participate. Patients will receive initial periodontal examination and treatment if necessary. Patients must be classified as ASA I or ASA II according to the American Society of Anesthesiologists and demonstrate both a Full Mouth Plaque Score (FMPS) and a Full Mouth Bleeding Score (FMBS) <20% to be included in the study. Patients with any contraindications for periodontal surgery, who are currently taking anticoagulants or corticosteroids, or who smoke >10 cigarettes/day will be excluded from the study.

Clinical Methodology

A computerized randomization program will assign participants to one of two groups. Patients will be block-randomized to ensure a balance between all the operators. Both groups will undergo SECTG surgery for root coverage utilizing an autogenous graft obtained from the patient's palate. Details regarding the preparation of the recipient site and the specific root coverage technique will not be dictated by the experimental protocol as they will have no effect on the outcomes being measured. The palate is anesthetized with 2% lidocaine (1:100000 epinephrine) by greater palatine nerve block, nasopalatine nerve block, and local infiltration as needed, ensuring not to inject anesthetic into the graft tissue. Prior to harvesting the graft, the

thickness of the palatal tissue at the donor site will be measured via transgingival probing (or ultrasound device). Graft tissue will be harvested according to the Single-Incision Technique described by Hurzeler.

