Surgical Technique: The donor area of the palate is located between the root of the canine and the palatal root of the first molar. Its lateral border is positioned approximately 2 mm from the gingival margin and its medial border is dictated by the position of the palatal neurovascular bundle which can be found 7, 12, or 17 mm from the cemento-enamel junction of the correspondent teeth, depending on whether the palatal vault is shallow, average, or high, respectively. A single horizontal incision, whose length corresponds to the required length of the graft, is made at 90° to the underlying bone approximately 2 mm from the gingival margin with a #15 blade. The blade is then angled at approximately 135° to the bone and a split-thickness dissection is started within that first incision, towards the median of the palate. As the incision is advanced, the angle of the scalpel is further flattened until it is nearly parallel to the bone surface. Elevation of the overlying tissue should be avoided to reduce the risk of perforation while making this incision. Split-thickness dissection continues until the necessary dimensions of the graft are obtained, ideally maintaining 1.0-1.5 mm of overlying tissue. The SECTG is separated from the surrounding tissue via incisions to the bone surface at the mesial, distal, and medial borders of the graft. The graft is detached from the bone with a periosteal elevator and placed on a saline-soaked gauze until it is transferred to the recipient site.

The length, width, and thickness of the graft, the thickness of the remaining palatal tissue, and the length of the palatal incision will be measured with digital calipers to the nearest 0.1 mm. Palatal incisions will be closed with cyanoacrylate. Immediately following completion of the

surgical procedure, Group A will receive PBM treatment of the donor site with Er:YAG laser according to the parameters shown to induce maximal proliferation of human gingival fibroblasts (Energy Setting: 80 mJ, Pulse Rate: 25 Hz, Duration: 30 s). Group B will receive sham treatment with the laser unit turned off.

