At the one-week post-operative appointment, the participants will return their VAS questionnaires and any remaining Ibuprofen tablets. They will be asked to fill out a modified Oral Impacts on Daily Performance (OIDP) questionnaire to assess the effect of the palatal wound on their oral-health related quality of life during the first post-operative week. A clinician who did not perform the surgery and is blinded to which treatment group the patient belongs will assess the donor site at the one- and two-week post-operative appointments according to a modified early-wound healing index (MEHI) proposed by Fickl (a variation of the EHI originally conceived by Wachtel) as well as the healing index (HI) of Landry, Turnbull and Howley. Participants will return for a six-week post-operative appointment, during which tissue thickness at the donor site will be measured via bone sounding and a histological specimen will be harvested with a tissue punch. Tissue samples will immediately be submerged in a solution of 10% neutral buffered formalin. Clinical photographs will be taken at all appointments.

Risks

There is the risk in both the test and control groups of post-operative complications that are associated with any periodontal surgery including intraoral pain or discomfort, bleeding,

infection, swelling and bruising. There is also a risk that the desired outcome, either partial or complete root coverage (depending on the severity and classification of the initial recession defect), may not be achieved by the surgical procedure.

Potential Benefits

If Er:YAG photobiomodulation of the palatal donor site results in improved and/or faster healing of the tissue or less post-operative discomfort, then patients requiring SETGs will benefit from a shorter and more pleasant healing period following their surgery. Also, as the effects of Er:YAG PBM on healing have never been investigated in human studies, the information gained from this study would help direct future research on this topic.

Consent Process

Patients of the Graduate Periodontics Clinic at the University of Manitoba who require SECTG and who meet the eligibility requirements will be asked personally if they would like to be a part of the project. After being given a brief description of the research, if the patient is interested, they will be provided a written summary of the study and a consent form to sign if they would like to take part.

Data Security

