All data will be recorded based on the subject's assigned number after they have agreed to participate and have signed the consent form. Their names and contact information will be stored in a secure, locked location at the U of M Graduate Periodontics Clinic. Findings from the

study may be published or presented in a public forum. Participants' names will not be used and no identifying details revealed.

STATISTICAL ANALYSIS PLAN

The study will be blinded at the level of data collection and data assessment. The primary outcome for this study is the patients' post-operative discomfort from the palatal donor site during the first week following surgery. This is assessed by VAS scores and analgesic consumption. Friedman's two-way ANOVA test will compare the change in VAS scores over time within each treatment group. Mann-Whitney U test will compare the difference in VAS scores between the two groups at each time point as well as the differences in total analgesic use between the two groups. The secondary outcomes are healing of the donor site and the palatal wound's effect on the patients' OHQoL. Healing is assessed by MEHI and HI scores and by tissue thickness. Wilcoxon Signed Ranks test will compare the change in MEHI and HI scores from week one to week two within each treatment group. Mann-Whitney U test will compare the differences in MEHI and HI scores between the treatment groups as well as the differences in tissue thickness at six weeks post-operatively between the groups. OHQoL is assessed by OIDP scores. The differences in OIDP scores between treatment groups is compared with Mann-Whitney U test. The level of significance is $p \leq 0.05$. IBM SPSS Statistics for Windows (Version 25.0) is used for analysis.

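### Six-week donor-site thickness is compared without using the pre-harvest thickness already measured: a cheap precision option, not an error, whose gain depends on an unstated sample size and correlation

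*Combined protocol and SAP*

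**What the plan says.** In the Statistical Analysis Plan, donor-site healing is one of two secondary outcomes: "Healing is assessed by MEHI and HI scores and by tissue thickness". For thickness, the planned Mann-Whitney test covers "the differences in tissue thickness at six weeks post-operatively between the groups". No covariate is named, and no estimate or interval is planned alongside the test.

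The protocol collects thickness on three occasions:

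- **Before harvest** (Clinical Methodology): "thickness of the palatal tissue at the donor site will be measured via transgingival probing (or ultrasound device".
- **At surgery, before laser or sham** (Surgical Technique): graft thickness is recorded, together with "the thickness of the remaining palatal tissue, and the length of the palatal incision will be measured with digital calipers".
- **At six weeks** (the follow-up description in Clinical Methodology): "tissue thickness at the donor site will be measured via bone sounding".

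Between the first and last of these, the tissue itself changes. Surgical Technique states "The graft is detached from the bone with a periosteal elevator", with the overlying flap "ideally maintaining 1.0-1.5 mm of overlying tissue".

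On allocation, Clinical Methodology says "Patients will be block-randomized to ensure a balance between all the operators". Baseline thickness is not named as a balancing factor. The documents state no sample size, SD, effect size or correlation between the two thickness readings.

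**The concern.** Both groups have a thickness reading taken before the randomized treatment is applied, and the outcome is a later thickness reading at the same site. If patients with thicker tissue before harvest tend to have thicker tissue at six weeks, part of the spread in the outcome is predictable. A comparison that ignores the baseline then carries noise it could have removed.

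In a pilot this is one of the few ways to sharpen an estimate without more patients. The protocol's stated benefits include guiding later research, and an adjusted difference in mm with an interval serves that purpose better than a rank-test p-value alone. What is at stake is precision on this one measure. The primary discomfort outcome, the MEHI and HI scores and the OIDP scores are unaffected.

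**Working it through.** **Inputs.** The planned test, the p ≤ 0.05 level and the timing of the readings come from the documents. The plan has no figure of its own to reproduce here. Assumed: two-sided testing, equal arms of n = 10, 15 or 20 (N = 2n), bivariate normal data with equal SDs, and r from 0 to 0.7. Widths are in outcome SDs. Since the SAP plans a test and no interval, width serves only as a yardstick of precision.

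**Step 1: interval width.** Let c4(v) be the expected ratio of the sample SD to the true SD on v degrees of freedom.

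- Unadjusted t interval: w0 = 2 × t(N-2) × c4(N-2) × sqrt(2/n). At n = 15: 2 × 2.0484 × 0.9911 × 0.3651 = 1.48.
- ANCOVA at r = 0: w1 = 2 × t(N-3) × c4(N-3) × sqrt(2/n) × K. K is the average inflation from chance baseline imbalance, close to sqrt((N-3)/(N-4)). At n = 15: 2 × 2.0518 × 0.9908 × 0.3651 × 1.0187 = 1.51.
- ANCOVA at correlation r: w1 × sqrt(1 - r²).
- Break-even: r = sqrt(1 - (w0/w1)²).

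| Per arm | w0 | w1 | Break-even r | r = 0 | 0.2 | 0.3 | 0.5 | 0.7 |
|---|---|---|---|---|---|---|---|---|
| 10 | 1.853 | 1.915 | 0.25 | +3.3% | +1.2% | -1.4% | -10.5% | -26.2% |
| 15 | 1.483 | 1.512 | 0.20 | +2.0% | -0.1% | -2.7% | -11.7% | -27.2% |
| 20 | 1.272 | 1.290 | 0.17 | +1.4% | -0.6% | -3.2% | -12.2% | -27.6% |

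The last five columns give the change in width from w0. As a cross-check on variance instead of width, the break-even is 1/sqrt(N-3): 1/sqrt(17) = 0.24, 1/sqrt(27) = 0.19 and 1/sqrt(37) = 0.16. Width break-evens are slightly higher because they also charge for the lost degree of freedom.

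**Step 2: power against the planned test.** Simulated with 20,000 replicates per cell (Monte Carlo SE up to 0.004), a true difference of 0.8 SD and the asymptotic Mann-Whitney test:

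| Per arm | Mann-Whitney (any r) | Analysis | r = 0 | 0.2 | 0.3 | 0.5 | 0.7 |
|---|---|---|---|---|---|---|---|
| 10 | 0.380-0.390 | rank ANCOVA | 0.363 | 0.378 | 0.386 | 0.439 | 0.575 |
| 15 | 0.537-0.549 | rank ANCOVA | 0.535 | 0.544 | 0.559 | 0.638 | 0.779 |
| 15 | 0.537-0.549 | ANCOVA | 0.556 | 0.563 | 0.584 | 0.671 | 0.830 |
| 20 | 0.667-0.673 | rank ANCOVA | 0.663 | 0.682 | 0.702 | 0.770 | 0.894 |

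At r = 0, a separate run of ANCOVA against Mann-Whitney gave 0.378 against 0.386 at 10 per arm and 0.544 against 0.538 at 15. The two are therefore about level. Rank ANCOVA breaks even at r of roughly 0.2 to 0.3 for 10 to 15 per arm. With a 0.5 SD difference at 15 per arm, Mann-Whitney power is 0.251-0.256, and rank ANCOVA rises from 0.248 at r = 0 to 0.403 at r = 0.7.

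**Step 3: baseline measurement error.** Random error in the baseline reduces r to r × sqrt(reliability). With assumed reliabilities of 0.8 and 0.6, a true r of 0.5 acts as 0.45 or 0.39. At 15 per arm the width change is then -8.8% or -6.0%, instead of -11.7%. This does not cover a systematic offset between probing and ultrasound.

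**The case against.** The strongest case is that nothing is wrong: the unadjusted comparison is valid, and choosing between valid analyses is partly preference. The benefit also cannot be shown from the documents, which give neither N nor r. Graft removal and the change of method both point towards a modest r. All of this stands, and it is why the point is only an option to consider.

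Three further objections stand in part:

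- **Normality.** The calculations assume normal data with equal SDs, which favours ANCOVA. Skewed or coarse probe readings were not examined, so a rank-based check should be kept.
- **Choice of covariate.** The remaining tissue thickness recorded at surgery also precedes laser or sham, and is closer to the state from which healing starts. Choosing the pre-harvest value is a judgement. What matters is naming one covariate in advance.
- **Timing.** Recruitment was planned for Fall 2018 to Spring 2020 and the document is dated October 16, 2020. The chance to prespecify may have passed.

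A reader might infer that the planned test is biased because it ignores baseline. Randomization protects it, and adjustment here concerns precision. A reader might also infer that adjusting helps only when r exceeds 0.2. That figure is tied to about 15 per arm and to an unadjusted t interval as comparator. It moves with N, and it is not a threshold for ANCOVA against the planned Mann-Whitney test.

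**Conclusion.** The point holds as a cheap improvement to one component of a secondary outcome. A reading taken before treatment is collected and left unused, and adjusting for it has a small, known downside.

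Under normal data and 10 to 20 per arm, the effect on interval width is slightly adverse at r = 0, trivial at r = 0.3, and material from about r = 0.5. Whether r reaches that level is not established. The documents therefore do not support a claim that the plan loses substantial power; they support only that it may. Confidence is medium, because N, r, the effect size and the distribution are all assumed.

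**What to change.** Prespecify one ANCOVA of six-week thickness with treatment and pre-harvest donor-site thickness as the single covariate, and report the adjusted difference in mm with its 95% CI. Keep one rank-based analysis, either rank ANCOVA or the planned Mann-Whitney test, as the sensitivity check for skewed or coarse readings. Record for each patient whether the baseline was taken by probing or ultrasound.

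A bare change score is not a safe substitute while r is unknown. At 15 per arm, 0.8 SD and equal SDs, its t-test power is 0.430 at r = 0.3, 0.562 at r = 0.5 and 0.781 at r = 0.7. The unadjusted t test has 0.557-0.571, and ANCOVA has 0.584, 0.671 and 0.830 at the same three correlations.

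The cost is SAP wording and one degree of freedom, with no new measurements beyond noting the baseline method. If the covariate proves non-prognostic, the interval is about 1.4%, 2.0% or 3.3% wider at 20, 15 or 10 per arm. If the data are already unblinded, keep the Mann-Whitney test as planned and label the ANCOVA supplementary.
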